9.2 Immunological (immunogenicity) analyses

9.2.1 Anti-bimekizumab antibody

ADAb will be assessed using a 3-tiered assay approach: screening, confirmatory and titration assay. Samples confirmed as positive within the confirmatory assay will be further evaluated for the presence of NAb specific to binding of bimekizumab to IL-17AA, IL-17FF or both.

ADAb (including positivity) will be summarized by BKZ treatment at each scheduled visit at which samples are collected.

Screening, confirmatory and titer cut points of the respective assays will be determined by the bioanalytical laboratory based either on commercially available drug-naïve samples or on the pre-dose samples of a given study. The relevant statistical reports will be provided as part of the bioanalytical reports. ADAb samples are analyzed on the SS, but are not analyzed when subjects are on a treatment other than BKZ. Subjects assigned to the placebo arm will have only their Baseline (study day 1) and Week 16 samples analyzed for ADAb.

The Screening cut point will be used to determine the ADAb status in the test sample as “Positive Screen” (PS) or “Negative Screen” (NS). For samples presenting anti-BKZ antibody levels that are PS, further confirmatory assay will be performed, and the result of which will be reported as either “Positive Immunodepletion” (PI) or “Negative Immunodepletion” (NI).

ADAb status for each visit will be derived as follows:

- Samples that are either NS or PS and NI will be defined as ADAb negative.
- Sample values that are either NS or PS and NI and where the BKZ concentration exceeds the validated ADAb assay drug tolerance limit (200 µg/mL) will be defined as inconclusive.
- Sample values that are PS and PI will be defined as ADAb positive (regardless of availability of a titer value)
- Missing if it does not go into one of the above categories.

PI samples will be titrated, and the ADAb titer (reciprocal dilution factor including MRD) reported. The PI samples will also be subject to a neutralizing assay to evaluate whether the anti-BKZ antibody neutralizes the target binding of bimekizumab (IL17A or IL17F or both) in-vitro. The following rule will be implemented for by-visit ADAb summaries where applicable:

- If the ADAb sample is collected within ± 14 days (inclusive) relative to the visit date at which the drug was administered (or ± 14 days from a scheduled visit at which dosing was not performed), the ADAb result for that sample will be associated with the scheduled visit and summarized accordingly. This will include unscheduled assessments (if a dose was administered at an unscheduled visit). Samples collected outside this window will be excluded from the by-visit ADAb summaries and will be listed only.

The rule above will apply to by-visit summaries only; all other summaries of ADAb status will use all available data (scheduled and unscheduled). This rule will not apply for the ET or SFU visits. Thus, all ADAb data obtained at these visits will be included in the by-visit summaries.

In addition, the anti-BKZ antibody status will be further classified as outlined below:

- **Category 1: Pre ADAb negative – treatment emergent ADAb negative:** Includes subjects who are negative at Baseline and antibody negative at all sampling points post treatment (including SFU), one post-baseline missing/inconclusive sample is allowed for subjects with pre-ADAb negative sample. This group also includes subjects who have missing/inconclusive pre-treatment sample (eg, either missing/inconclusive or insufficient volume) at baseline with all post-Baseline samples as ADAb negative.
- **Category 2: Pre ADAb negative – treatment emergent ADAb positive:** Includes subjects who are negative at Baseline and antibody positive at any sampling point post treatment (including SFU). This group also includes subjects who have a missing pre-treatment sample (either missing or insufficient volume) at Baseline with one or more ADAb positive post-treatment samples.
- **Category 3: Pre ADAb positive – treatment emergent reduced ADAb:** Includes subjects who are positive at Baseline, and antibody negative at all sampling points post treatment (including SFU).
- **Category 4: Pre ADAb positive – treatment unaffected ADAb positive:** Includes subjects who are positive at Baseline and are positive at any sampling point post treatment (including SFU) with titer values of the same magnitude as Baseline (ie, less than a predefined fold difference from the Baseline value). For the purpose of this study, this is set at an increase of less than the validated Minimum Significant Ratio (MSR) of 2.07-fold from Baseline.

- **Category 5: Pre ADAb positive – treatment boosted ADAb positive:** Includes subjects who are positive at Baseline and are positive at any sampling point post treatment (including SFU) with increased titer values compared to Baseline (greater than or equal to a predefined fold difference increase from Baseline value which is defined within the validation of the assay). For the purposes of this study, this is set at an increase greater than or equal to the validated Minimum Significant Ratio (MSR) of 2.07-fold from Baseline.

Note: For any subject who is positive at Baseline and positive at a post-Baseline time point, but for whom titers are not available to determine treatment unaffected or treatment boosted status, the subject will be considered as treatment boosted (ie, Category 5), assuming no other samples are available.

- **Category 6: Inconclusive:** Includes subjects who have a positive pre-treatment sample and some post-treatment samples are missing, while other post-treatment samples are ADAb negative or missing.
- **Category 7: Total treatment-emergent:** Category 2 and 5 combined: Includes subjects who are pre ADAb negative – treatment emergent ADAb positive (Category 2) and pre ADAb positive – treatment boosted ADAb positive (Category 5).
- **Category 8: Total prevalence of pre-ADAb positivity:** (Categories 3, 4, 5 and 6 combined): Subjects that are tested ADAb positive at Baseline.
- **Category 9: Missing:** Includes subjects who have a negative or a missing/inconclusive pre-treatment sample and some post-treatment samples are missing/inconclusive, while other post-treatment samples are ADAb negative or missing.

All the following analyses will be prepared on the SS:

- Summary tables displaying the number and percentage of subjects with ADAb status (positive, negative, or missing) at the time of each visit by treatment group (160mg Q4W) will be provided. For the placebo arm, the by-visit summary of ADAb positive status will include a summary of subjects with ADAb status (positive, negative, or missing) at Baseline and Week 16. For the overall summary at any visit (only applicable to 160mg Q4W dose arm), two summaries will be presented: one that will exclude data obtained at the SFU visit and will include data obtained at Baseline and one that will include data obtained at both the SFU visit and at Baseline. Subjects who rolled over to the OLE study will not have a SFU visit per study protocol. For these subjects, the ‘overall ADAb status including SFU’ will then be considered as being identical to the ‘overall ADAb status up to Week 16’.

For the overall ADAb status, a subject will be classified as:

- Positive if the subject has at least one positive sample at any time in the treatment period (regardless of having missing /inconclusive data)
- Negative if the subject has all the samples negative or only one missing/inconclusive sample with negative ADAb samples up to the timepoint of interest
- Missing if the subject has missed more than one sample result for ADAb assessment (or have more than one inconclusive sample) and all other available ADAb samples are negative during the period of interest (If there are $\geq 95\%$ of subjects included in the non-missing groups, the missing group will not be displayed on the table).

The above summary table displaying the number and percentage of subjects in each of the ADA_b status (positive, negative, total of positive and negative, missing) will be repeated for the subgroup of Japan.

- A summary table displaying the number and percentage of subjects in each of the ADA_b status (positive, negative, total of positive and negative, missing) by concomitant medications (use of cDMARDs at entry, use of methotrexate at entry, use of oral/systemic corticosteroids at entry) will be provided (overall summaries only).
- A table displaying the number and percentage of subjects with the first occurrence of any ADA_b positivity during the study (ie, including Baseline visit) will be summarized. This summary will include the following categories:
 - Any ADA_b+: ADA positive sample regardless of category during the treatment period
 - ADA_b category 2: Pre ADA_b negative – treatment-emergent ADA_b positive
 - ADA_b category 5: Pre ADA_b positive – treatment-boosted ADA_b positive (if this category represents at least 10% of the subjects, otherwise results are to be merged with category 2). For this category, the first occurrence of a boosted result is considered.

The table will include the number and percentage of subjects with first occurrence of any ADA_b sample, and also subjects who are either treatment-emergent ADA_b positive or treatment-boosted ADA_b positive for the first time at the specified time point in the study and will include the cumulative number and percentage of subjects with treatment-emergent ADA_b positive results at each time point.

- A boxplot of the ADA_b titer by time of occurrence of ADA_b positivity will be created. The ADA_b titer results will be presented on the log-scale. The time represents the visit week for the ADA_b positive sample. Subjects who do not have any ADA_b positivity will be excluded from the plot.
- A summary table of the number and percentage of subjects in each of the 9 ADA_b categories will be tabulated.
- Figure summarizing the time to achieve ADA_b positivity and treatment-emergent ADA_b positivity on a cumulative basis (2 lines per plot) will be presented. Subjects will be considered to have an event at the time point at which an ADA_b result or treatment emergent ADA_b positive is first achieved. Treatment-emergent ADA_b in this plot will be based on ADA_b category 7 (total treatment-emergent ADA_b).

In the event that $\geq 10\%$ of subjects are classified as ADA_b category 5, the lines will be further split by the following categories (thus the plot will include 3 lines):

- ADA_b category 2: Pre ADA_b negative – treatment-emergent ADA_b positive
- ADA_b category 5: Pre ADA_b positive – treatment-boosted ADA_b positive
- Individual plots (1 plot per subject) of BKZ concentrations/ADA_b titer and the ACR50 response (based on NRI) will be created. Each time, all 3 endpoints will be plotted on the Y-axis by visit (X-axis) for the full treatment period, including SFU where a subject has not progressed into the OLE. Plots should be labeled and grouped into the 9 ADA_b categories and display vertical lines on the X-axis corresponding to the dosing incidences/visits.

- Individual plot (1 plot per subject) of BKZ concentrations/ADAb titer and PASI90 response will also be created similarly as described above.
- Spaghetti plots of ADAb titer (Y-axis) will be reported on the log-scale by visit (X-axis) for all ADAb positive subjects, including Baseline positive subjects. This plot will include the following ADAb categories:
 - ADAb category 2: Pre ADAb negative – treatment-emergent ADAb positive
 - ADAb category 5: Pre ADAb positive – treatment-boosted ADAb positive

Plots will be presented using a semi-logarithmic scale for the ADAb titers (ADAb negative samples will therefore be excluded from the plot). Furthermore, all ADAb titer values <100 will be represented as 1 in these plots.

- Figures will summarize efficacy response (ACR50, ACR20 and PASI90 responders based on NRI) versus ADAb titer quartiles. The X-axis will display the ADAb titer quartiles at Week 16 (categorized as negative, Q1, Q2, Q3 and Q4) and the y-axis will display percentage of ACR50 (ACR20 or PASI90) responders at Week 16. The plot will therefore display the percentage of ACR50 (ACR20 or PASI90) responders as a function of the number of subjects within each ADAb and titer categories. Subjects with negative ADAb results at Week 16 will be included in the 'negative' category on the X-axis.
- A figure summarizing time course of efficacy response (ACR50 responders based on NRI) for the BKZ 160mg Q4W group by the following ADAb groups (3 lines per plot) will be created:
 - ADAb positive - defined as subjects having at least 2 ADAb positive samples during the study (including baseline and SFU) regardless of other ADAb negative samples and/or missing or inconclusive samples
 - ADAb negative - defined as subjects for whom either (1) all samples (including baseline and SFU) are ADAb negative and there are no missing or inconclusive samples, (2) only 1 sample is ADAb positive and all other samples (including baseline and SFU) are ADAb negative or missing/inconclusive or 3) only one sample is missing/inconclusive and the remaining ADAb samples are negative.
 - Missing - defined as subjects who do not fulfil the criteria for one of the 2 groups listed above.

If $\geq 95\%$ of subjects are included in the non-missing groups, the missing group will not be displayed in the figure.

The data will also be presented in a tabular format. The figure and table will be repeated for ACR20 and PASI90.

Note: for efficacy by ADAb status summary up to a particular timepoint (Weeks 16), only ADAb data up to the timepoint of interest will be utilized in deriving the overall ADAb status during that period. The percent of subjects in each of the ADAb categories considered for efficacy sub-group analyses will be summarized.

- All individual subject-level ADAb results will be listed including the Screening assay, confirmatory assay, ADAb status, and titers if applicable. Note, that titer results will only be

available, if the confirmatory assay is positive. The listing will also include flags for ADA_b measurements that were excluded from the by-visit summaries. The reason for exclusion will be one of the following:

- Sample collected out of window relative to current dose (or visit),
- More than one sample obtained at the same visit.
- Finally, if more than 10% of the ADA_b results have been excluded from the table summaries, the ADA_b excluded results will be listed in the same listing as the one mentioned in [Section 9.1](#) for excluded PK results.

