4.2.2.1 Non-responder imputation

For binary endpoints, the non-responder imputation (NRI) analysis, also described above as the primary composite estimand, will consider the following subjects as “non-responders” for the timepoint of interest:

- Subjects with missing data at the timepoint of interest. In the case of ACR50, nonresponse is imputed if ACR50 cannot be derived (ie, derived as “missing”) based on available ACR components. (Section 8.1.1).

- Subjects remaining in the study at the timepoint of interest but discontinuing study treatment before the timepoint of interest (data after IE).
- Subjects with missing Baseline value (for composite or non-composite binary variables based on change(s) from Baseline of continuous endpoint(s)).

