9 PHARMACOKINETICS AND IMMUNOLOGICAL (IMMUNOGENICITY) ANALYSES

9.1 Pharmacokinetics

Pharmacokinetic variables will be analyzed for all subjects in the PK-PPS.

Only subjects treated with BKZ will be included in the PK analyses. The Baseline observation for the Placebo group will be the Week 16 pre-dose observation. PK variables will be summarized at each scheduled visit under the “BKZ 160mg Q4W” column. BKZ concentrations will also be summarized similarly for the subgroup of Japan.

No imputation will be used for missing samples. However, if plasma concentration measurements are below the level of quantification (BLQ), then for the calculation of the derived statistics, the result will be set to $\frac{1}{2}$ of LLOQ (ie, $\frac{1}{2} * 0.250 = 0.125 \text{ug/mL}$). Descriptive statistics including number of values, geometric mean, its 95% CI, geometric CV, mean, SD, median, minimum, and maximum. Geometric mean and its 95% CI, geometric CV, mean and SD will be calculated if applicable will be calculated if at least $\frac{2}{3}$ of the values of interest is above the LLOQ and number of values ≥ 3 ; otherwise, only number of values, median, minimum, and maximum will be presented.

In addition, geometric mean of BKZ plasma concentration time curves (with its 95% CI) will be plotted on linear and semi-logarithmic scales for all subjects dosed with 160mg Q4W.

The table summaries and figures will be primarily repeated by anti-BKZ antibody status (positive, negative, or missing) for the total BKZ 160mg Q4W concentration data. The Missing group will not be displayed if $\geq 95\%$ of subjects are categorized in the non-missing groups.

The ADA b status (positive, negative, or missing) will be considered in a cumulative manner at each time point:

- a subject will be counted as positive from the first visit at which the subject achieved a positive ADA b sample result to the end of the treatment period (regardless of any missing/inconclusive or negative ADA b sample result).
- If a subject has only negative ADA b samples or only one missing/inconclusive sample with negative ADA b samples up to that timepoint, the subject will be classified as negative. An exception remains for the Baseline Visit where only one sample could be available. If the sample is missing/inconclusive, then the sample will be classified as being negative for the cumulative ADA b status.
- Otherwise, the subject will be classified in the missing ADA b category.

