9.2.2 Neutralizing anti-bimekizumab antibodies

NAb will be assessed using IL-17AA- and IL-17FF-specific assay method, respectively. NAb results will be positive or negative to each specific NAb assay or both.

All NAb results derived from samples with drug concentrations > the drug tolerance limits of the NAb assays (100µg/mL) will be labeled 'inconclusive'. All inconclusive results will be regarded as missing.

Subjects will be assigned an overall Neutralizing anti-BKZ antibodies (NAb) classification, inclusive of Baseline and post-Baseline results from NAb assay:

- NAb negative: No NAb positive samples for IL-17AA and IL-17FF at Baseline or post-Baseline. This group will also include subjects who have only 1 missing sample and all other available samples during the period of interest are negative. Subjects who are NAb negative will be classified as follows:
 - ADA_b positive / NAb negative: ADA_b positive subjects who are 1) NAb negative for all available ADA_b positive samples or 2) with only 1 missing NAb sample and all other evaluated ADA_b positive samples are NAb negative.
 - ADA_b negative: if the subject has all the samples as ADA_b negative or only 1 missing/inconclusive sample with all other available samples as negative ADA_b. Note that ADA_b negative samples are not subject to the neutralizing assay.
- NAb positive: One or more positive samples (IL-17AA positive, IL-17FF positive, or both) at Baseline or post-Baseline (regardless of missing samples). Subjects who are NAb positive will be further classified as follows:
 - Positive for IL-17AA only: 1 or more positive samples for IL-17AA at Baseline or post-Baseline. No positive samples for IL-17FF
 - Positive for IL-17FF only: 1 or more positive samples for IL-17 FF at Baseline or post-Baseline. No positive samples for IL-17AA
 - Positive for both IL-17AA and IL-17FF: 1 or more positive samples for both IL-17AA and IL-17FF at Baseline or post-Baseline

- NAb Missing: more than one relevant NAb samples are missing/inconclusive and other available NAb samples during the period of interest are negative, missing or insufficient sample left for NAb testing.

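### In the efficacy time course by ADAb group, a subject with a single positive sample is classed as ADAb negative however many other samples are missing

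*SAP*

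**What the plan says.** SAP Section 9.2.1 plans "A figure summarizing time course of efficacy response (ACR50 responders based on NRI) for the BKZ 160mg Q4W group", split into ADAb positive, ADAb negative and Missing, with a matching table and repeats for ACR20 and PASI90.

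- Positive is "defined as subjects having at least 2 ADAb positive samples during the study (including baseline and SFU").
- Negative has three routes: (1) all samples negative and none missing; (2) "only 1 sample is ADAb positive and all other samples (including baseline and SFU) are ADAb negative or missing/inconclusive"; (3) one sample missing or inconclusive and the rest negative.
- Missing is everyone else. The group is dropped from the figure when at least 95% of subjects are in the other two.

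Elsewhere the SAP defines the same status differently:

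- Section 9.2.1, overall ADAb status: "Positive if the subject has at least one positive sample at any time in the treatment period", whatever else is missing. More than one missing or inconclusive sample with the rest negative is Missing.
- Section 9.1, PK summaries: "a subject will be counted as positive from the first visit at which the subject achieved a positive ADA b sample result".
- Section 9.2.2, used for the efficacy figure by neutralizing-antibody (NAb) status: a subject is ADAb negative "if the subject has all the samples as ADA_b negative or only 1 missing/inconclusive sample" with the others negative. One positive sample rules this out.

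Section 4.2.2.1 lists who is a non-responder under NRI. The list includes "Subjects with missing data at the timepoint of interest" and "Subjects remaining in the study at the timepoint of interest but discontinuing study treatment before the timepoint of interest (data after IE").

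**The concern.** Route (2) treats absent samples as if they supported negativity, and only for subjects who already have a positive result. Under Section 9.2.1 a positive sample has passed both the screening and the confirmatory assay, so the lone positive is not merely a screening signal. A subject with one such result and four missing samples is called negative, while a subject with one negative result and four missing samples is called Missing.

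The display is meant to show whether antibodies go with loss of response. Subjects who stop early have fewer chances of a second positive sample and are non-responders under NRI at later visits. If they had one positive sample, the rule counts them in the negative group. In addition, two parallel efficacy-over-time figures, one by ADAb and one by NAb status, would use the label ADAb negative for different sets of people.

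**Working it through.** **Classification.** Section 2.2.3.5 has ADAb assessed at every visit except Screening, which gives five samples to Week 16 (Baseline, Weeks 4, 8, 12 and 16). With N = negative, P = positive, M = missing or inconclusive, in visit order:

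| Pattern | Time-course rule | Overall-status rule |
|---|---|---|
| N-M-M-M-M | Missing | Missing |
| N-N-N-M-M | Missing | Missing |
| P-M-M-M-M | Negative | Positive |
| N-P-M-M-M | Negative | Positive |
| N-N-P-M-M | Negative | Positive |
| N-N-N-N-P | Negative | Positive |
| N-P-P-M-M | Positive | Positive |

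Of the 3^5 = 243 possible patterns, 5 × 2^4 = 80 contain exactly one positive. All 80 are negative under the time-course rule and positive under the overall-status rule, and no other pattern changes group. With the SFU sample the count is 6 × 2^5 = 192 of 729. These are counts of patterns, not weighted by how likely each is.

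**Direction.** Let the ever-positive group have n subjects and R responders, and the remaining group m subjects and S responders. Moving d non-responders changes the rates from R/n to R/(n − d), which is higher, and from S/m to S/(m + d), which is lower. If antibodies reduce response, the displayed gap is therefore too small.

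**Size (illustration only).** The SAP attaches no figure to this display and gives no ADAb prevalence or dropout rate. From Section 2.4 come 260 BKZ subjects, and from Section 2.4.1 an assumed BKZ ACR50 rate of 26%. My assumptions are:

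- NRI ACR50 of 28% if never positive and 21% if ever positive, a gap of 7.0 points. The overall rate is then 25.2% to 26.6%, near the planned 26%.
- 20% to 40% of subjects ever positive.
- Single-positive dropouts make up 5%, 10% or 20% of the ever-positive.
- All other ever-positive subjects share one response rate.

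Example, 30% ever positive and 10% of those single-positive dropouts: n = 78, R = 78 × 0.21 = 16.38; m = 182, S = 182 × 0.28 = 50.96; d = 7.8. Positive rate 16.38/70.2 = 23.3%; negative rate 50.96/189.8 = 26.8%; gap 3.5 points.

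| Ever positive | 5% dropouts: d, gap | 10%: d, gap | 20%: d, gap |
|---|---|---|---|
| 20% | 2.6, 5.5 | 5.2, 4.0 | 10.4, 0.4 |
| 30% | 3.9, 5.3 | 7.8, 3.5 | 15.6, −0.5 |
| 40% | 5.2, 5.0 | 10.4, 2.9 | 20.8, −1.5 |

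Single-positive completers move too. Suppose they are a further 20% of the ever-positive and respond like other positive completers. The gaps then become 4.4 to 5.3, 2.6 to 3.8 and −1.4 to 0.4, a small change. If they respond better than other positives, their move widens the gap instead.

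**The case against.** Requiring two positives is stated openly as this figure's own definition, and a stricter criterion meant to set aside transient positivity is a legitimate choice. That stands for the threshold. It does not justify reading unobserved samples as negative, because a missing sample cannot show that positivity was transient.

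The plan also limits missing samples. Under Section 2.3.2, subjects who only stop IMP return through Week 16, and those who leave the study have an early termination visit. Section 3.2.2 maps ADAb from that visit to the next ADAb visit. A subject last seen at Week 8 would often yield one more sample, and a second positive makes that subject positive. This reduces the number affected. It does not help subjects whose later samples are missed or not positive: they remain non-responders once off treatment and remain in the negative group.

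A reader might infer that the SAP hides an antibody effect across its efficacy analyses. The text does not support that:

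- The Week 16 ACR50 plot by ADAb category (Section 8.1.3) uses categories in which a subject who is negative at Baseline with any later positive counts as treatment-emergent positive.
- The titer-quartile figure uses the Week 16 result.
- The NAb figure keeps single positives out of its ADAb-negative group.
- The ADAb subgroup analysis (Sections 4.8 and 8.1.3) refers only to Section 9.2, so its definition is not stated either way.

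Finally, all subject-level ADAb results are listed, no test is attached to this figure, and immunogenicity falls under the other objectives.

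**Conclusion.** The point holds for one descriptive display: the ACR50, ACR20 and PASI90 time-course figure and table by ADAb group. Three things follow from the text alone. Missing samples are treated asymmetrically, the rule conflicts with the any-positive rule used for overall status and PK, and the label ADAb negative differs in meaning from the NAb efficacy figure. Given NRI, the shift caused by single-positive dropouts also has a fixed direction, towards showing no antibody effect.

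The size cannot be determined from the SAP. A reader might conclude that the gap would vanish or reverse, but this depends on the assumed inputs. In the illustration it takes 20% of ever-positive subjects being single-positive dropouts, for which the SAP gives no basis. A larger assumed gap shows the same dependence. Take 45% versus 30%, with 104 ever positive, 41.6 of them single-positive and 20.8 of those dropouts. The gap reverses to −1.3 points only if single-positive completers respond at 30% and repeat positives at (31.2 − 6.24)/62.4 = 40%. With one rate of 31.2/83.2 = 37.5% for all who stay, the negative group is at 78/197.6 = 39.5% and the gap is about +2.

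The rule should be corrected, but it does not threaten the trial's conclusions: the primary analysis and the testing hierarchy are not affected.

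**What to change.** Use the overall-status definition already in Section 9.2.1 for this figure and table. At least one positive sample up to Week 16 is positive; all samples negative, or only one missing or inconclusive with the rest negative, is negative; anything else is Missing.

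If the two-positive definition is kept as an additional display:

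- Limit route (2) so that a single positive with more than one missing or inconclusive sample is not negative. Of the 80 single-positive patterns, 5 × (6 + 4 + 1) = 55 have more than one missing sample.
- Show the group that receives these subjects even when it is under 5%. Moving them to Missing still takes non-responders out of the positive group, so they must stay visible.
- Give the negative group its own label, such as negative or single positive.

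In either case, reconcile the inclusion of SFU samples in the group definitions with the note later in Section 9.2.1 that restricts ADAb data to the timepoint of interest (Week 16). Under that limit a subject first positive at Week 16 cannot reach two positives, and OLE entrants have no SFU sample.

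The cost is some SAP wording and one derivation. The downside is that subjects with one transient, Baseline-only or first Week 16 positive join the positive group in the main display, although those first positive at Week 16 had no detected antibody for most of the curve. The optional second display can show how much this matters.
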